(Generalized Anxiety Disorder-7, GAD-7), traumatic stress (PTSD Checklist-Civilian, PCL-C), stress (Perceived Stress Scale, PSS), and a quality of life measure (EuroQol Five Dimensions Questionnaire, EQ-5D), as well as drop stick reaction testing, and dynamometry for grip strength. Measures will be collected at an enrollment visit (V1), and the intervention will begin 1-14 days thereafter. BP and heart rate (HR) recording will be repeated prior to the start of the 7th session. Post-intervention data collections will be obtained at 1-7 days (V2), 4-6 weeks (V3, primary outcome), and 12-14 weeks (V4) following completion of the intervention. The primary outcome will be differential change in the systolic and diastolic BP from V1 to V3. Following V4, those in the NCC group will be offered the opportunity to cross over to receive a course of HCC, and will continue to be followed for data collections at 1-7 days (V5), 4-6 weeks (V6), and 12-14 weeks (V7) after completing their crossover HIRREM sessions. We will utilize linear mixed models (LMMs) to contrast longitudinal changes in systolic and diastolic blood pressure between the HCC and NCC groups. Mean contrasts will be used to compare the changes in blood pressures between groups from V1 to V3, our primary test of efficacy. Additional mean contrasts will be constructed to evaluate the consistency of any benefit of HIRREM through subsequent visits beyond V3. Comparisons of changes in all secondary outcomes will be assessed in a similar fashion.

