10 participants (5 female), mean age 47.2 (SD 20.1) with a resting supine blood pressure of >130/90 were enrolled in an ongoing, open label, IRB-approved feasibility study of HIRREM for diverse neurological/psychophysiological symptoms and disorders. After an initial HIRREM assessment of brain frequencies and amplitudes, baseline data collection included symptom inventories for insomnia (ISI), depression (CES-D), and anxiety (GAD-7), along with physiological and functional measures. Blood pressure and heart rate was continuously recorded while supine, with spontaneous breathing. Subjects then received 17.7 (5.9) HIRREM sessions (90-120 minutes each). Sessions consisted of 5-9 protocols, from 6-40 minutes each, with up to two sessions per day, and were received over a total of 20.1 (28.6) days, but only 10.2 (3.0) in-office days. All measures were repeated after completion of the intervention, 14.4 (15.4) days after the final HIRREM session. Analysis of autonomic cardiovascular regulation included spectral analysis for calculation of multiple standard measures of HRV (including SDRR and rMSSD), baroreflex sensitivity (BRS, HF Alpha, Sequence Up SBP, Sequence Down SBP, and Sequence ALL), and arterial pressure (systolic, SAP, diastolic, DAP, and mean, MAP). There were no dropouts among those with hypertension, and no reported serious adverse events for any of the HIRREM research studies to date.

Table 1:

Key Autonomic Cardiovascular Outcomes				
Measure (Units)	Mean Value Baseline (SE)	Mean Value Post-HIRREM (SE)	Mean Change (SE)	p value
Up SBP (ms/mmHg)	10.6 (3.0)	16.3 (3.9)	5.7 (1.3)	p = 0.001
SDRR (ms)	42 (7.1)	57 (9.7)	15.1 (7.0)	p = 0.049
SAP (mmHg)	151.7 (6.0)	136 (6.9)	-15.1 (5.5)	p = 0.018
DAP (mmHg)	97.2 (2.8)	81 (1.8)	-16.2 (3.1)	p < 0.001
MAP (mmHg)	116.5 (2.9)	100.9 (2.0)	-15.6 (4.3)	p = 0.004

Table 2:

Key Behavioral Outcomes				
Measure	Mean Value Baseline (SD)	Mean Value Post-HIRREM (SD)	Mean Change (SD)	p value
ISI	8.1 (7.2)	3.3 (3.2)	-4.8 (4.6)	p = 0.009
GAD-7	7.2 (3.8)	2.2 (2.4)	-5.0 (4.3)	p = 0.06
CES-D	14.5 (11.7)	7.1 (3.8)	-7.4 (9.8)	p = 0.07

Figure 1:

[figure not shown]

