In addition to reduction in self-reported symptoms, and improved network connectivity on whole brain, resting MRI studies, all measures HRV and BRS measures increased, showing improved autonomic cardiovascular regulation, with increased parasympathetic influence, and SAP decreased, suggesting improved sympatho-vagal balance (Table 3, below) (Catherine Tegeler, Shaltout, Lee, & Tegeler, 2016; Charles Tegeler, Catherine Tegeler, Jared Cook, Lindsay Howard, et al., 2016; Charles Tegeler, Catherine Tegeler, Jared Cook, Sung Lee, et al., 2016).

Table 3:

Key Autonomic Cardiovascular Outcomes				
Measure (Units)	Mean Value Baseline (SE)	Mean Value Post-HIRREM (SE)	Mean Change (SE)	p value
HF Alpha (ms/mmHg)	17.61 (2.56)	27.28 (3.84)	9.67 (3.09)	p = 0.005
Up SBP (ms/mmHg)	13.06 (1.87)	21.45 (2.99)	8.39 (3.04)	p = 0.011
Down SBP (ms/mmHg)	14.43 (1.78)	22.03 (2.60)	7.61 (2.42)	p = 0.005
Sequence All (ms/mmHg)	13.75 (1.74)	21.41 (2.37)	7.66 (2.20)	p = 0.006
SDNN (ms)	50.98 (5.40)	62.97 (5.23)	11.98 (3.46)	p = 0.003
rMSSD (ms)	32.76 (4.33)	45.98 (5.33)	13.22 (3.00)	p < 0.001
SAP (mmHg)	131.26 (3.18)	125.39 (2.92)	-5.87 (1.91)	p = 0.020

While blood pressure reduction and HRV improvement in these studies could also be secondary to reduced insomnia and anxiety, it may reflect reduced sympathetic tone to blood vessels associated with reduced allostatic load. Additional studies are warranted to investigate the mechanism of the changes associated with this highly promising intervention.

Specific to pre-hypertension, which is the focus for this trial, review of participant data from the ongoing Developmental Study (IRB#00017651) identified 66 participants for whom there was V1 and V2 data, whose baseline BP readings placed them in the category of having pre-hypertension (mean systolic 127.5, diastolic 81.2, and MAP 97.0 mmHg). Participants received a mean of 16.4 HIRREM sessions, over a mean total of 22.4 days, with a mean of 9.5 days actually in the office. Although these participants had only mildly increased BP at baseline (just considered as pre-hypertension), data collection at baseline (V1), and 1-2 weeks after completion of the HIRREM intervention (V2) showed

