After informed consent is obtained, blood pressure will be obtained to confirm eligibility. Those with BP less than 120 mmHg systolic and 80 mm Hg diastolic, or greater than 140 mmHg systolic or 90 mmHg diastolic, will be considered as screening failures, and will not move on to the remaining enrollment visit activities. For those confirmed to have an eligible baseline blood pressure reading, a brief medical history will be obtained, randomization will be completed, and baseline study measures obtained, prior to the start of the intervention. Those scheduled for an enrollment visit will also be provided a copy of Appendix B, Handout to Study Participants, and/or a welcome email with details.

Inclusion Criteria:

Men and women, ≥ 18 years of age, with pre-hypertension, who have systolic BP ranging from 120-139 mm/Hg, or who have diastolic BP ranging from 80-89 mm/Hg.

Exclusion Criteria:

Blood pressure values that are outside of the range for prehypertension at the enrollment visit

Unable, unwilling, or incompetent to provide informed consent

Physically unable to come to the study visits, or to sit comfortably in a chair for up to two hours at a time

Prior diagnosis of hypertension

Ongoing need for medical treatment for hypertension, or for the use of medications commonly used for treatment of hypertension
Known cardiovascular disease
Known seizure disorder
Known or anticipated pregnancy (females of childbearing age will be tested for pregnancy prior to randomization)
Severe hearing impairment (because the subject will be using headphones during the interventions)
Ongoing need for treatment with opiate, benzodiazepine, or anti-psychotic medications, anti-depressant medications such as SSRI, SNRI, or tricyclic, and sleep medications such as zolpidem or eszopiclone
Anticipated and ongoing use of recreational drugs, alcohol, or energy drinks
Ongoing need for treatment with thyroid medications

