with all measures repeated. Data collected at the V3 visit will comprise the primary outcome data for the study. A final data collection visit (V4) will occur 12-14 weeks after completion of the intervention, with repeat of the outcome measures, but no brainwave assessment. At V4, official study involvement is complete for those in the HCC group, while those randomized to the NCC group will be offered an opportunity to be scheduled to receive a course of HCC. Those who opt to do so will receive a course of acoustic stimulation linked to brainwaves, as described for the HCC group, and will continue to be followed for data collections at 1-7 days (V5), 4-6 weeks (V6), and 12-14 weeks (V7), as done during the initial intervention period, after completing their crossover HCC sessions.

Enrollment Visit:

Informed consent is obtained, and blood pressure is then obtained. Since all participants will have been documented to have prior blood pressure values that meet the parameters for prehypertension, and in light of variability associated with visits to the doctor, or other factors, if blood pressure values are too high, or too low on the initial measurements the potential participant will be allowed to rest for at least 3 minutes, and the blood pressure will be repeated. Those who still have blood pressure values less than 120 mmHg systolic pressure, and diastolic pressure less than 80 mmHg, and thus do not meet criteria for pre-hypertension, will be considered as screen failures. Those with blood pressure that is still higher than 140 mmHg systolic or 90 mmHg diastolic, will be also be considered as screen failures. They will not be assigned a study number, and will be excluded from further participation. Those with blood pressure values that are too high will also be advised to follow up with their medical provider. For those who meet blood pressure goals, notification of group assignment is made, and all baseline measures are collected, including a brainwave assessment. If not already completed via a REDCap link, a brief medical history form will be completed (Appendix C). The V1 visit will require about 2 hours of time.

Intervention Period:

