Heart rate is measured as beat-to-beat intervals (RRI) recorded by pulse-wave recording, and will be analyzed using custom software developed by Matlab. Data can be loaded and viewed, and a subset of the data can be selected to avoid artifacts during device placement or removal. Outlier identification is performed by determining all IBIs which demonstrate a 30% difference from the mean of the previous four samples. Such outliers are removed from the data set. HRV statistics that are generated include mean, variance, SDNN, rMSSD, VLF, LF, HF, TP, LF/HF, sample asymmetry, sample entropy, and coherence ("Heart rate variability: standards of measurement, physiological interpretation and clinical use. Task Force of the European Society of Cardiology and the North American Society of Pacing and Electrophysiology," 1996). All of the algorithms for computation of these parameters are derived from information or source code from the Physionet archive. Data are saved to Excel spreadsheets for further statistical analysis by study team members.

Blood Pressure (BP):

For evaluation of blood pressure (BP) values that will be used to qualify for participation in the study, and for analysis of the primary outcomes, BP measurements will be obtained using an automated oscillometric blood pressure device. BP will be obtained in the left arm, with the participant sitting

comfortably, and the left arm resting on a desk/table. Three samples will be obtained and the last two averaged to get the value that will be used as the reading for that visit (Kaplan NM, 2010).

Insomnia:

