Reaction testing will be evaluated by a drop-stick, clinical reaction time apparatus. It is constructed from a meter stick covered in friction tape with gradations. The modified meter stick is fixed to a weighted rubber cylinder. The apparatus is placed between the thumb and index finger of the subject and released at a random time during a countdown. The subject catches the apparatus and the distance fallen (cm) is converted to reaction. Following two practice trials, subjects perform eight trials, and a mean distance value is used for analysis. This is repeated with a second set of 8 trials later during the enrollment visit, and the mean distance value from the second trial will be used as the baseline value. Use of the average distance from the second set of trials will be used as the baseline value so as to avoid the impact of learning effect for this test. This simple clinical measure has been evaluated by Eckner et al, and demonstrated utility in testing comparable to computerized testing methods (Eckner, Kutcher, & Richardson, 2010). Our pilot data demonstrate improved reaction testing associated with use of HIRREM for athletes with persisting post-concussion symptoms (C. H. Tegeler et al., 2016).

Grip Strength:

Grip strength will be evaluated using a hydraulic hand dynamometer (Baseline Hydraulic Hand Dynamometer). The greatest force generated during three trials will be used for analysis (Roberts et al., 2011).

Statistical Analysis:

Continuous variables will be summarized with standard descriptive statistics, such as quartiles, means, and standard deviations, while categorical variables will be summarized with percentages and frequencies. LMMs will be employed to contrast longitudinal changes in systolic and diastolic blood pressure between the HCC and NCC groups. Mean contrasts will be used to compare the changes in blood pressure between groups from V1 to V3, our primary test of efficacy. Comparisons of changes in all secondary outcomes will be assessed in a similar fashion. Assumption and computation diagnostics will be assessed for all model fits (Cheng, Edwards, Maldonado-Molina, Komro, & Muller, 2010), and model adjustments and outcome variable transformations will be made as necessary. Data will be analyzed using SAS v9.4 (SAS Institute, Inc., Cary, NC) or the R Statistical Computing Environment.

Participant Compensation:

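### The primary V1-to-V3 blood pressure contrast states no adjustment for V1 blood pressure; prespecifying the V1-adjusted V3 difference is a cheap improvement

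*Combined protocol and SAP*

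**What the plan says.** The Abstract (Methods) states: "We will utilize linear mixed models (LMMs) to contrast longitudinal changes in systolic and diastolic blood pressure between the HCC and NCC groups". The Statistical Analysis section then fixes the primary test: "Mean contrasts will be used to compare the changes in blood pressure between groups from V1 to V3, our primary test of efficacy". The Overview defines the outcome the same way, as differential change from V1 to V3 in systolic and diastolic pressure.

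No section lists the model's fixed effects, enters V1 pressure as a covariate, constrains the arms to a common V1 mean, or stratifies randomisation on pressure. The only mention of adjusting a model comes with the diagnostics, where changes are allowed as needed.

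On timing, Participants/Subjects says: "For those confirmed to have an eligible baseline blood pressure reading, a brief medical history will be obtained, randomization will be completed". Enrollment Visit says: "For those who meet blood pressure goals, notification of group assignment is made, and all baseline measures are collected". The Blood Pressure (BP) section uses one cuff method for "values that will be used to qualify for participation in the study, and for analysis of the primary outcomes". If the first reading is out of range, "the potential participant will be allowed to rest for at least 3 minutes, and the blood pressure will be repeated". The plan does not say which reading is then the V1 value.

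**The concern.** With about 10 completers per arm, a V1 difference of a few mmHg between arms can easily arise by chance. A change-score contrast removes the whole of that difference. If V3 tracks V1 with a slope below 1, it removes too much, and the arm that happened to start higher appears to improve more.

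The Importance section names effect-size estimates for larger trials as a product of this study, and Number of Subjects says no sample size could be calculated. The estimate therefore matters at least as much as the test, and an avoidable dependence on the V1 gap would pass into later planning. The wording also admits several models that give different answers on the same data.

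**Working it through.** **Arm size.** The plan has no power figure to reproduce. Its enrolment target is 20 × 1.2 = 24 for 20 completers (20/0.8 would give 25; the difference does not matter here). I use 10 per arm.

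**1. What the ordinary model estimates.** Three simulated trials (10 per arm, V1-V4, complete data) gave, at V3:

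| V1 gap | Group-by-visit LMM | Change-score difference | V3 on arm and V1 | Common-V1-mean LMM |
|---|---|---|---|---|
| -2.77 | 0.3156 | 0.3156 | -0.593 | -1.151 |
| 2.74 | -7.8639 | -7.8639 | -7.039 | -6.448 |
| -4.08 | -2.4288 | -2.4288 | -2.657 | -3.849 |

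The second and third columns agree to four decimals. With gap = HCC minus NCC at V1, unadjusted minus adjusted = -(1 - fitted slope) × gap. In the first row, 0.3156 + 0.593 = 0.909 = (1 - 0.67) × 2.77.

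**2. Slopes implied by the pilot tables** (Specific Relevant Pilot Data). Slope = (SE1² + SE2² - SEchange²) / (2 × SE1²); intervals use t with n - 2 df.

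- Systolic, Table 1, n = 10 (6.0, 6.9, 5.5): (36 + 47.61 - 30.25)/72 = 0.74, 95% CI 0.02 to 1.46.
- Systolic, Table 3, n = 18 (3.18, 2.92, 1.91): (10.11 + 8.53 - 3.65)/20.22 = 0.74, 0.45 to 1.03.
- Diastolic, Table 1, n = 10 (2.8, 1.8, 3.1): (7.84 + 3.24 - 9.61)/15.68 = 0.09, -0.42 to 0.61.

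The diastolic interval excludes 1; the systolic intervals do not.

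**3. Size of a chance V1 gap.** Assumed, because the documents give no seated SDs: systolic SD 10-12, diastolic SD 8-9, correlation 0.6 between the two. Means of 127.5/81.2 are those of the 66-participant pre-hypertension series. The entry window in Participants/Subjects was then imposed, leaving V1 SDs of 6.2-6.8 systolic and 5.5-5.9 diastolic. One standard error of the gap is SD × √(2/10) = 2.8-3.1 mmHg systolic and 2.5-2.7 diastolic. Under normality, about a third of randomisations give a gap of 1 SE or more, and about 5% give 2 SE or more.

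**4. Shift in the unadjusted estimate at a 1-SE gap** = (1 - slope) × V1 SD × √(2/10).

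- Systolic at 0.74: 0.26 × 6.16 × 0.447 = 0.72; range 0.7-0.8 mmHg, about 10-11% of the 95% half-width (6.4-7.7). Over slopes 0.3-0.8 it is 0.5-2.1.
- Diastolic at 0.09: 0.91 × 5.54 × 0.447 = 2.25; range 2.2-2.4 mmHg, about 25% of the half-width (8.9-9.8). At 0.61 it is 1.0; over slopes 0.3-0.8 it is 0.5-1.9.

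For scale, the uncontrolled pilot changes at the later follow-up were -8.6 systolic and -5.2 diastolic. After adjustment the simulated shift is within 0.1 mmHg of zero.

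**5. Error rate and precision** (100,000 simulated trials per setting, no treatment effect, equal pre-truncation SDs at V1 and V3; change-score t test against V3 on arm and V1).

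- Overall type I error: 4.9-5.2% for both tests.
- At a 1-SE gap: about 5% for both.
- At a 2-SE gap, unadjusted: 6.0-6.5% systolic (slope 0.74) and 13-19% diastolic (slope 0.09; the range covers two choices of V3 SD). Adjusted: about 5-6%.
- Variance ratio, adjusted to unadjusted: systolic 1.006-1.012 at 0.74; diastolic 0.76-0.78 at 0.09 and 0.95-0.97 at 0.61.

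**6. Dropout.** With 12 per arm enrolled and 2 per arm lost at random before V3, the unadjusted shift at a 1-SE gap is 0.65-0.75 systolic and 2.0-2.2 diastolic. The adjusted mixed model is within 0.03. Variance ratios are 1.00-1.01 and 0.79-0.80.

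**The case against.** A change contrast from a mixed model is a legitimate primary analysis: unbiased over randomisation, with type I error held. The text names no fixed effects, so a common-V1-mean model would satisfy it and would already adjust; what is shown is under-specification, not a decision against adjustment. For systolic pressure the gain is close to nil. The material claim is diastolic and rests on one row of 10 people, described as "10 participants (5 female), mean age 47.2 (SD 20.1) with a resting supine blood pressure of >130/90 were enrolled". Their mean diastolic pressure of 97.2 lies above this trial's ceiling of 90, and they were recorded supine in an open-label series.

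Table 1 is also rough. Its MAP row back-calculates to a slope of (8.41 + 4.00 - 18.49)/16.82 = -0.36, and its systolic means fall by 151.7 - 136 = 15.7 while -15.1 is printed. Taking the change SE from the printed p values moves the systolic slopes to 0.78 and 0.66. Precision depends on the assumed SDs: using the pilot tables' own SDs without the entry window gives variance ratios of 0.87-0.98 systolic and 0.35 diastolic. Finally, sampling error at 10 per arm exceeds all of these shifts.

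All of this stands as a limit on size, and the 13-19% figure belongs to gaps seen in only about 5% of randomisations. It does not remove the point. The primary model is left open among analyses that give different answers, and the ordinary one depends on a chance gap that an already collected reading can remove.

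**Conclusion.** The concern holds as a recommended improvement, not as a validity error. On the ordinary reading, the primary estimate carries (1 - slope) times whatever V1 gap this trial draws. At a 1-SE gap that is 0.7-0.8 mmHg systolic, which is minor, and 2.2-2.4 mmHg diastolic at the pilot slope, or 1.0 at its upper confidence limit, which may be material. Adjustment brings no systolic precision gain at slope 0.74; a diastolic gain is likely.

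The algebra is exact for complete data. The sizes rest on assumed seated SDs, an assumed systolic-diastolic correlation, and slopes from small, supine, uncontrolled series. Confidence in the sizes is therefore moderate, and the diastolic figure is the least certain.

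**What to change.** - Prespecify the primary estimate, for systolic and diastolic pressure, as the HCC minus NCC difference at V3 adjusted for V1 pressure. Use either a mixed model with V1 and V1-by-visit as covariates or one with a common V1 mean across arms, and name which.
- Name V3 regressed on arm and V1 as the fallback if the model does not converge.
- State that baseline is the qualifying V1 reading taken before randomisation is completed, and which reading counts when the out-of-range repeat is used.

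The cost is analysis-plan wording and a few lines of code, with no new data. The covariate form over V2-V4 adds three V1 slopes and has six covariance parameters if unstructured. The common-mean form over V1-V4 has ten, the same as an unstructured group-by-visit model. Adjustment uses one or more degrees of freedom. Its worst case is about 4-6% more variance if the V1-V3 correlation is high or the V1 spread is narrow; the ceiling is 1/(20 - 4) = 6.25%. With the dropout above, the fallback's variance relative to the unadjusted contrast is 1.03-1.04 systolic (slope 0.74) and 0.82-0.83 diastolic (slope 0.09).

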experienced by the HCC group. Technologists will interact with the participant during the sessions, as they would with HIRREM sessions, requesting that some portions are with eyes open, and others with eyes closed. As with the real HIRREM sessions, if eyes closed segments the participant may recline and drift to sleep, while with eyes open, they may just relax, or engage in activities such as reading, or a word search. In order to achieve comparability with the HCC group, including potential effects of exposure time to the environment and study personnel, those randomized to the NCC group will also receive between 8-16 sessions. The number of sessions for the NCC group will be randomly assigned via a second randomization, following their assignment to the NCC group.

Safety:

Evidence to date indicates that the HIRREM intervention is potentially high benefit and low risk. Based on experience reported by Brain State Technologies, garnered from provision of case management support, feedback from their clients, and feedback from the HIRREM provider community, as well as from our IRB-approved studies at WFSM (now over 450 participants to receive HIRREM), we are not aware of any serious adverse events resulting from HIRREM sessions. A few participants undergoing HIRREM have reported experiencing emotions, both positive and negative, primarily during initial sessions. These have been similar to the range of emotions one might experience in the course of everyday life events, and have been transient, resolving over a few minutes or hours, to several days. In the course of providing HCC to over 450 individuals participating in one of five IRB-approved research studies at WFSM, such mild symptoms have been estimated to occur in less than 5 percent of participants, and none have experienced prolonged or intense changes in emotional state, or required additional treatment. All HIRREM sessions are administered by Technologists who have been certified in the procedure, including guidelines for addressing emotional releases that may occur. In the event that emotional releases are prolonged or intense, individuals would be advised to see a mental health professional for additional evaluation or treatment, or if acute, will be referred to the Emergency Department. There have been no instances in the > 440 subjects participating to-date of prolonged or intense changes in emotional state. There are no anticipated risks associated with listening to ambient nature sounds.

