Other Data Collection, Measures, and Process:

A series of measures will be collected at the enrollment visit (V1), as well as at three post-intervention visits for all participants.

Demographics:

Demographic information will include embedded elements to allow calculation of the Charlson Comorbidity Index Score (Charlson et al., 2008).

Autonomic cardiovascular Regulation [Blood Pressure (BP), Heart Rate (HR), Heart Rate Variability (HRV), Baroreflex Sensitivity (BRS), and Blood Pressure Variability (BPV)]:

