The principal investigator will be responsible for the overall monitoring of the data and safety of study participants. The principal investigator will be assisted by other members of the study staff.

Any collected patient identifying information corresponding to the unique study identifier will be maintained on a separate master log. The master log will be kept secure, with access limited to designated study personnel. Following data collection subject identifying information will be destroyed at the earliest opportunity, consistent with data validation and study design, producing an anonymous analytical data set. Data access will be limited to study staff. Data and records will be kept locked and secured, with any computer data password protected.

Reporting of Unanticipated Problems, Adverse Events, or Deviations:

Any unanticipated problems, serious and unexpected adverse events, deviations or protocol changes will be promptly reported by the principal investigator or designated member of the research team to the IRB and sponsor or appropriate government agency if appropriate.

Appendices

A:

Insomnia Severity Index (ISI)
Center for Epidemiological Studies Depression Scale (CES-D)
Generalized Anxiety Disorder 7-Item (GAD-7)
Epworth Sleepiness Score (ESS)
PTSD Checklist for Civilians (PCL-C)
Perceived Stress Scale (PSS)
Pittsburgh Sleep Quality Index (PSQI)
AUDIT-C
Quality of Life Scale (QOLS)

B:

Handout for Study Participants

C:

Medical History/Screening Form

References:

- Alvarsson, J. J., Wiens, S., & Nilsson, M. E. (2010). Stress recovery during exposure to nature sound and environmental noise. *Int J Environ Res Public Health*, *7*(3), 1036-1046. doi:10.3390/ijerph7031036
- Bastien, C. H., Vallieres, A., & Morin, C. M. (2001). Validation of the Insomnia Severity Index as an outcome measure for insomnia research. *Sleep Med*, *2*(4), 297-307. doi:S1389945700000654 [pii]
- Blanchard, E. B., Jones-Alexander, J., Buckley, T. C., & Forneris, C. A. (1996). Psychometric properties of the PTSD Checklist (PCL). *Behav. Res. Ther*, *34*(8), 669-673. doi:0005-7967(96)00033-2 [pii]

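### The protocol makes no stated provision to record or tabulate non-serious adverse events in either arm, so transient reactions to the sessions would go uncounted

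*Combined protocol and SAP*

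**What the plan says.** The section Reporting of Unanticipated Problems, Adverse Events, or Deviations holds the only rule about adverse events: "Any unanticipated problems, serious and unexpected adverse events, deviations or protocol changes will be promptly reported by the principal investigator". The recipients are the IRB and, where appropriate, the sponsor or a government agency. Data and Safety Monitoring adds who is in charge, "The principal investigator will be responsible for the overall monitoring of the data and safety of study participants", but no form, question or schedule.

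The Safety section names one reaction to the intervention: "A few participants undergoing HIRREM have reported experiencing emotions, both positive and negative, primarily during initial sessions". It says that these "have been transient, resolving over a few minutes or hours, to several days" and that "such mild symptoms have been estimated to occur in less than 5 percent of participants". For severe cases it gives management advice: "In the event that emotional releases are prolonged or intense, individuals would be advised to see a mental health professional for additional evaluation or treatment", with emergency referral if acute. For the control it says: "There are no anticipated risks associated with listening to ambient nature sounds".

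On data collection the protocol says: "A series of measures will be collected at the enrollment visit (V1), as well as at three post-intervention visits for all participants". The measures described under that heading are physiological, questionnaire-based and functional. None is an adverse-event query, log or grading. The Statistical Analysis section covers descriptive summaries, mixed models for blood pressure and the same approach for secondary outcomes, with no adverse-event table.

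Between session 1 and V2, the only scheduled measurement in both arms is blood pressure and heart rate before session 7. Under HIRREM/Ambient Sound Sessions, the number of HCC sessions depends on a running review of brain patterns and of self-reported symptoms such as sleep and stress. The number of NCC sessions is set by a second randomization.

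**The concern.** The protocol describes a reaction it expects to see and says when it tends to occur, but tells nobody to write it down. A mild reaction of a kind already described is neither serious nor unexpected, so the reporting rule does not reach it, and no other section does. A transient reaction that is not noted at the time cannot be recovered at analysis.

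The Importance section says the study will confirm feasibility and might justify larger trials. The Safety section calls the intervention low risk, relying on developer experience and earlier studies and on a rate that is only estimated. This trial has a randomized control intended to match environment, time and staff contact. It could describe these reactions against that control, but as written it has no count to report.

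**Working it through.** **1. Does any section collect the named reaction?**

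- Reporting section: sets a threshold for prompt external reporting. A mild, already described reaction does not meet the serious-and-unexpected criterion in either arm.
- Safety section: advice and referral for severe reactions, with no instruction to record.
- Data-collection sections: no adverse-event item.
- Statistical Analysis: no adverse-event summary.

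**2. Would the scheduled inventories catch it?** The course may last up to 4 weeks and V2 falls 1 to 7 days after the last session. The longest gap from session 1 is 28 + 7 = 35 days. The first six sessions are given two per day on three consecutive days, so reactions in the initial sessions fall at the start of that gap. The shortest course (8 sessions in 4 half days, V2 one day later) gives about 4 + 1 = 5 days. GAD-7, PCL-C, PSS and CES-D at V2 to V4 could show lasting worsening by arm. They do not count an episode that ended within hours or days of an early session.

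**3. Is noticing equal between arms?** Symptom review during the course is stated for HCC, where it helps set session number. No such review is stated for NCC, whose session number is randomized. NCC technologists are told to interact as they would in HIRREM sessions, which narrows the difference but does not give both arms the same question.

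**4. What would recording yield?** Inputs: up to 24 enrolled and 20 completers, 10 per group (Number of Subjects). The plan's figure reproduces as 20 × 1.20 = 24. I assume equal allocation, so 12 per arm. The under-5% figure is used as a ceiling, because it covers positive and negative emotions together.

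Expected reactions = n × p; chance of at least one = 1 − (1 − p)^n:

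- n = 12, p = 0.05: 0.6 expected; 1 − 0.95^12 = 46%.
- n = 10, p = 0.05: 0.5 expected; 1 − 0.95^10 = 40%.
- n = 12, at assumed lower rates of 1% and 2%: 11% and 22%.
- n = 24, p = 0.05 (no dropout, every NCC participant crosses over): 1.2 expected; 1 − 0.95^24 = 71%.
- n = 20, p = 0.05 (planned completers, all controls crossing over): 1.0 expected; 1 − 0.95^20 = 64%.

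One-sided 95% upper bound after zero events = 1 − 0.05^(1/n):

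- n = 10: 26%
- n = 12: 22%
- n = 20: 14%
- n = 24: 12%

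For zero events to bring the bound to 5%, 0.95^n must be at most 0.05. So n is at least ln 0.05 / ln 0.95 = 58.4, that is 59 exposed.

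For k of 12 against 0 of 12, two-sided Fisher p = 2 × C(12,k) / C(24,k). With k = 4 this is 2 × 495 / 10,626 = 0.093; with k = 5 it is 2 × 792 / 42,504 = 0.037. Five reactions against none would be needed to reach 0.05.

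**The case against.** The strongest reply is that the rule does what such rules do: it sets a threshold for prompt external reporting, and limiting that to serious and unexpected events is normal. That stands. A reader might infer that the threshold itself is the error, but the gap is the absence of a separate collection rule.

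The reply continues that the trial is not blind to symptoms. The inventories are repeated in both arms and compared by group, the HCC course includes review of self-reported status, and severe reactions lead to referral. That also stands. The documents therefore do not support saying that such reactions are never captured, that no symptom check occurs before V2, or that harms cannot be compared by arm at all. What escapes is the count of transient, non-serious reactions.

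A reader might also infer that the same reaction would be treated as expected in HCC and unanticipated in NCC. The protocol does not define an unanticipated problem, and a mild reaction fails the serious-and-unexpected criterion in both arms. Only the narrower point survives: spontaneous mentions may be noticed unequally.

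Finally, the trial is too small to check the safety figure even with full recording, and it states no safety objective. Both are true. They limit the gain to description, but they do not explain why a reaction the protocol itself describes should go unrecorded when recording costs little.

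**Conclusion.** The point holds in a limited form: there is no stated provision to record or tabulate non-serious adverse events in either arm. Transient early-session reactions would depend on informal notice and would not reach the analysis.

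The size is modest. At the 5% ceiling, 0.6 reactions are expected among 12 HCC participants, with a 46% chance of at least one. Recording would not confirm the under-5% figure, since zero events bounds the rate only at 22% for 12 exposed, and at 12% for 24 under no dropout and full uptake of an optional crossover. Nor should 0.6 be read as expected harms: the figure mixes positive and negative emotions, and the negative share is not given.

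The conclusion rests on the text available. Consent pages are removed and the contents of Appendices B and C are not shown, but neither appendix is described as an adverse-event tool. The primary blood pressure analysis is unaffected. This is an inexpensive improvement to make before enrolment, not a flaw in the efficacy design.

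**What to change.** Leave the reporting rule as the criterion for prompt external reporting and add a separate collection rule beside it:

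- Ask the same fixed, open question in both arms at each session, at the existing stop before session 7, and at V2 to V4 (V5 to V7 after crossover).
- Log every adverse event, expected or not, with onset, duration, intensity, action taken and session number.
- Add one descriptive table to the Statistical Analysis section, by randomized arm and separately for crossover HIRREM exposure, giving participants with at least one event and exact binomial intervals. State that no test is planned.

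The cost is one short form, completed by technologists already present, and one table. The downside is a few minutes per contact and more minor events reported in both arms. Nothing in the intervention, the visit schedule or the management of reactions needs to change.
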